Subjects must have received prior treatment with approved drugs for tumors harboring these aberrations.

• Histology agnostic cancers other than pancreas and colorectal adenocarcinoma (see above; Phase 1 and 2)

Subjects must have progressed on or be intolerant of all standard of care therapies that result in a median progression free survival benefit of ≥ 8 weeks, or overall response rate of $>5\%$.

Columbia University Irving Medical Center
Herbert Irving Comprehensive Cancer Center
AAAS4165_Version Date: 07/07/2021

4. ECOG performance status of 0 or 1
5. Age \geq 18 years
6. Adequate hematological and end-organ function (test results from within 14 days prior to initiation of study treatment):
 - ANC $\geq 1.5 \times 10^9/L$ without granulocyte colony-stimulating factor support
 - WBC count $\geq 2.5 \times 10^9/L$ (2500/ μL)
 - Lymphocyte count $\geq 0.5 \times 10^9/L$ (500/ μL)
 - Platelet count $\geq 100 \times 10^9/L$ (100,000/ μL) without transfusion
 - Hgb $> 9.0 \text{ g/dL}$
 - AST, ALT, and alkaline phosphatase (ALP) $\leq 2.5X$ upper limit of normal (ULN), unless elevated secondary to biliary obstruction from the pancreas mass and amenable to decompression prior to initiation of therapy
 - Serum total bilirubin $\leq 1.5X$ ULN, unless in patients with known Gilbert disease ($\leq 3X$ ULN), or unless elevated secondary to biliary obstruction from the pancreas mass and amenable to decompression prior to administration of investigational therapy
 - Albumin $\geq 3.0\text{g/dL}$
 - Creatinine within ULN or calculated creatinine clearance (CrCl) $>50 \text{ mL/min}$ using the Cockcroft-Gault formula
 - INR and aPTT $\leq 1.5X$ ULN except for those who are on stable anticoagulation for at least three months.
7. Measurable disease according to IM-RECIST and tumor accessible for fresh biopsy if ten adequate paired biopsied specimens have not been procured (Phase 1)
8. Negative pregnancy test

Women of childbearing potential must have a negative serum pregnancy test at screening and must agree to use an effective form of contraception from the time of the negative pregnancy test until a minimum of 3 months after the last dose of study drug. Effective forms of contraception include abstinence, hormonal contraceptive (injectable or implantable) in conjunction with a barrier method, or a double barrier method. Women of non-child-bearing potential must have been postmenopausal for ≥ 1 year or surgically sterile.

9. Birth control agreement

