23. Grade \geq 3 hemorrhage or bleeding event within 28 days prior to initiation of study treatment

24. Prior autologous stem cell, allogeneic stem cell, or solid organ transplantation

25. History of malignancy

Patient may not have a history of malignancy other than PDA within 2 years prior to screening, with the exception of those with a negligible risk of metastasis or death (e.g., 5-year overall survival of $> 90\%$), such as adequately treated carcinoma *in situ* of the cervix, non-melanoma skin carcinoma, localized prostate cancer, ductal carcinoma *in situ*, or Stage I uterine cancer.

26. Recent vaccination

Patients may not have been treated with a live, attenuated vaccine within 4 weeks prior to initiation of study treatment, or anticipate the need for such a vaccine during treatment with atezolizumab or within 5 months after the last dose of atezolizumab.

27. History of severe allergic anaphylactic reactions to chimeric or humanized antibodies or fusion proteins

28. Known allergy or hypersensitivity to 4-aminoquinoline compounds or any of the study drug excipients

29. Recent immunosuppressive treatment

Patients may not have been treated with systemic immunosuppressive medication (including, but not limited to, corticosteroids, cyclophosphamide, azathioprine, methotrexate, thalidomide, and anti-tumor necrosis factor alpha agents) within 2 weeks prior to initiation of study treatment, or

Columbia University Irving Medical Center
Herbert Irving Comprehensive Cancer Center
AAAS4165_Version Date: 07/07/2021

anticipate the need for systemic immunosuppressive medication during the course of the study, with the following exceptions:

- Patients who received mineralocorticoids (e.g., fludrocortisone), corticosteroids for chronic obstructive pulmonary disease or asthma, or low-dose corticosteroids for orthostatic hypotension or adrenal insufficiency are eligible for the study if receiving equivalent to < 10mg of prednisone daily.
- Patients who received a one-time pulse dose of systemic immunosuppressant medication are eligible for the study after approval from the Principal Investigator.

30. Inability to swallow medication or malabsorption condition that would alter the absorption of orally administered medications

31. History of retinal pathology

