7.2.2 Medications Prohibited

- Live, attenuated vaccines (e.g., FluMist®) are prohibited within 4 weeks prior to initiation of study treatment, during treatment with atezolizumab, and for 5 months after the last dose of atezolizumab.
- Systemic immunostimulatory agents (including, but not limited to, interferons and interleukin 2) are prohibited within 12 weeks or five half-lives of the drug, whichever is longer, prior to initiation of study treatment and during study treatment because these agents could potentially increase the risk for autoimmune conditions when given in combination with atezolizumab.
- Systemic immunosuppressive medications (including, but not limited to, cyclophosphamide,

Columbia University Irving Medical Center
Herbert Irving Comprehensive Cancer Center
AAAS4165_Version Date: 07/07/2021

azathioprine, methotrexate, and thalidomide) are prohibited during study treatment because these agents could potentially alter the efficacy and safety of atezolizumab.

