8.3.1 Cobimetinib-associated adverse events

For specific guidelines on how to respond to adverse events associated with cobimetinib, see Appendix 1.

The following adverse events are classified as identified risks associated with cobimetinib: serious retinopathy, left ventricular dysfunction, severe hemorrhage, rhabdomyolysis, and pneumonitis. The following adverse events are classified as potential risks for cobimetinib: severe hepatotoxicity (Grade ≥ 3), impaired female fertility, and teratogenicity and developmental toxicity. In addition, there is the possibility of drug-drug interactions in patients treated with cobimetinib. Clinical and safety data were reported that included monotherapy and combination

studies, of which key adverse events are summarized here, but for a complete review of the safety data please refer to the most current IB version.

Common (>10%) adverse events observed with Cobimetinib included bleeding, serious retinopathy, diarrhea, nausea, emesis, rash, pyrexia, chills, anemia, increased liver function enzymes, increased creatinine phosphokinase, and photosensitivity. Less common (1% - 10%) adverse events included decreased left ventricular ejection, risk of basal and squamous cell carcinoma, kertocanthoma, dehydration, hyponatremia, hypophosphatemia, hyperglycemia, and pneumonitis. Guidelines for treatment interruption or discontinuation in the case of adverse events are described in Appendix 1.

Cobimetinib should be permanently discontinued for:

- Grade 4 hemorrhage events attributed to cobimetinib
- Symptomatic or asymptomatic decrease of LVEF < 40% or $\geq 10\%$ absolute decrease from baseline after treatment break or recurrent symptomatic absolute decrease of LVEF < 10% (See Table 1 for details)
- Rhabdomyolysis or symptomatic CPK elevations not improving within 4 weeks of dose interruption
- Liver laboratory abnormalities not resolving to Grade ≤ 1 within 4 weeks of dose interruption or if Grade 4 liver laboratory abnormalities recur after initial improvement
- QTc increase meets values of both > 500 ms and > 60 ms change from pre-treatment values or 3rd occurrence of QTc > 500 ms during treatment and change from pre-treatment value remains ≤ 60 ms

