9.4.1.5 Pregnancy

If a female patient becomes pregnant while receiving the study drug or within 5 months after the last dose of study drug, a report should be completed and expeditiously submitted to Columbia University who will report on behalf of all sites to its collaborators, Genentech, Inc., and Halozyme.. Follow-up to obtain the outcome of the pregnancy should also occur. Abortion, whether accidental, therapeutic, or spontaneous, should always be classified as serious, and expeditiously reported as an SAE. Similarly, any congenital anomaly/birth defect in a child born to a female patient exposed to the cobimetinib, atezolizumab and/or Hydroxychloroquine should be reported as an SAE.

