9.4.4 Reporting to Genentech

Adverse events, serious adverse events (SAEs), AEs of Special Interest (AESIs), pregnancy reports (including pregnancy occurring in the partner of a male study subject), Product Complaints (with or without an AE) and other Special Situation Reports where the patient has been exposed to the Genentech Product, will be sent on a MedWatch form or CIOMS I form or on Genentech approved reporting forms to Genentech Drug Safety. Transmission of these reports (initial and follow-up) will be sent either electronically or by fax and within the timelines specified below:

• Serious Adverse Drug Reactions (SADRs)

Serious AE reports that are related to the Product shall be transmitted to Genentech within fifteen (15) calendar days of the awareness date.

• Other SAEs

Serious AE reports that are unrelated to the Product shall be transmitted to Genentech within thirty (30) calendar days of the awareness date.

• Pregnancy reports

While such reports are not serious AEs or ADRs per se, as defined herein, any reports of pregnancy, where the fetus may have been exposed to the Product, shall be transmitted to Genentech within thirty (30) calendar days of the awareness date. Pregnancies will be followed up until the outcome of the pregnancy is known, whenever possible, based upon due diligence taken to obtain the follow-up information.

• AESI reporting to Genentech

AESIs shall be forwarded to Genentech within fifteen (15) calendar days of the awareness date.

• Product Complaints

All Product Complaints (with or without an AE) shall be forwarded to Genentech within fifteen (15) calendar days of the awareness date.

A Product Complaint is defined as any written or oral information received from a complainant that alleges deficiencies related to identity, quality, safety, strength, purity, reliability, durability, effectiveness, or performance of a product after it has been released and distributed to the commercial market or clinical trial.

Special situation reports

In addition to all AEs, pregnancy reports and AESIs, the following Special Situations Reports should be collected and transmitted to Genentech even in the absence of an Adverse Event within thirty (30) calendar days:

Columbia University Irving Medical Center
Herbert Irving Comprehensive Cancer Center
AAAS4165_Version Date: 07/07/2021

- Data related to the Product usage during breastfeeding

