Hydroxychloroquine is a small water soluble compound (MW 433.95) that is dispensed in 200 mg tablets for oral administration. In healthy males, peak blood concentration was reached in 3.26 hours with a half life of 537 hours (22.4 days). The plasma peak concentration was reached in 3.74 hours with a half life of 2,963 hours (123.5 days). The long half-life can be attributed to extensive tissue uptake rather than through decreased excretion. In subjects taking the drug chronically for six months, renal clearance of the drug appeared similar.

Hydroxychloroquine is prescribed for Malaria, Rheumatoid Arthritis, and Systemic Lupus Erythematosus by an unknown mechanism.

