10. Fresh core tumor biopsy will be performed: (1) within 14 days of starting therapy but at least three days prior to starting therapy; (2) Cycle 1 week 3 (day 15-21); and (3) If the patient allows, at progression (within 4 days of discontinuation of therapy).
11. TSH, free T4, and AM cortisol will be assessed at screening, Day 1 of each cycle starting at C2, at end of study, and as clinically appropriate.
12. At screening, patients without a prior positive HIV test result will undergo an HIV test, unless not permitted per local regulations. Patients will also be tested for HBsAg, HBsAb, total HBcAb, and HCV antibody. If a patient has a negative HBsAg test and a positive total HBcAb test at screening, an HBV DNA test should be performed. If a patient has a positive HCV antibody test at screening, an HCV RNA test must also be performed to determine if the patient has an active HCV infection.
13. For women of child-bearing potential, a screening serum pregnancy test must be negative within 7 days of Day 1 of Cycle 1.
14. Peripheral blood mononuclear cells will be collected during screening, cycle 1 day 15, cycle 3 day 1, every eight weeks (+ 7 days), and at End-of-Service visit.
15. CT scan with contrast of the chest, abdomen, pelvis or CT chest and MRI of abdomen/pelvis, PET/CT, or appropriate imaging of disease site to assess tumor status will be performed. Imaging should be performed at the designated time for tumor assessment +/- 7 days. End of study needs not be performed if patient has radiological evidence confirming progression, but needs to be performed if patient coming off study for other reasons, except due to fatality.
Phase 1 –Imaging to be performed every 8 weeks (+ 7 days)
Phase 2 –Pancreas adenocarcinoma –Imaging to be performed every 8 weeks (+ 7 days)
Colorectal adenocarcinoma – Imaging to be performed every 12 weeks (+ 7 days)
Histology agnostic adenocarcinoma – Imaging to be performed every 8 weeks (+ 7 days)
16. The initial dose of atezolizumab will be delivered over 60 (+/- 15) minutes. Subsequent infusions will be delivered over 30 (+/-10) minutes if the previous infusion was tolerated without infusion-associated adverse events, or 60 (+/- 15) minutes if the patient experienced an infusion-associated adverse event with the previous infusion.
17. For pharmacokinetic (PK) analysis, whole blood for hydroxychloroquine and plasma for cobimetinib will be obtained on –
Cycle 1 Day 1 - Pre-morning dose, 1, 2, and 4 hours post-morning dose.

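### Female contraception may stop 3 months after the last dose, although the protocol's own pregnancy-reporting window runs to 5 months

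*Combined protocol and SAP*

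**What the plan says.** Section 5.1, item 8, requires women of childbearing potential to have a negative serum pregnancy test at screening and to use effective contraception from that test "until a minimum of 3 months after the last dose of study drug". No visible section asks for longer.

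Section 9.4.1.5 sets a longer reporting period: "If a female patient becomes pregnant while receiving the study drug or within 5 months after the last dose of study drug", a report must be sent expeditiously. Section 9.4.4 asks for reports of pregnancies in which the fetus may have been exposed to the product, allows 30 calendar days for sending them to Genentech, and adds: "Pregnancies will be followed up until the outcome of the pregnancy is known, whenever possible".

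On reproductive risk, Section 8.3.1 lists among the potential risks of cobimetinib "impaired female fertility, and teratogenicity and developmental toxicity", and Section 3.2.2 reports a potential for reproductive toxicity at therapeutically relevant exposures. Neither gives a duration.

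The protocol also uses 5 months elsewhere. A patient must not expect to need a live vaccine during atezolizumab treatment or "within 5 months after the last dose of atezolizumab" (Section 5.2, item 26), and Section 7.2.2 prohibits such vaccines "for 5 months after the last dose of atezolizumab".

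The Study Calendar schedules one pregnancy test: "a screening serum pregnancy test must be negative within 7 days of Day 1 of Cycle 1" (Table 10, footnote 13).

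**The concern.** The contraception rule is meant to prevent fetal exposure and the reporting rule to detect it. Both count from the last dose of study drug, and prevention ends first. A woman who does all that item 8 asks could conceive in the fourth or fifth month after her last dose, and the protocol would want that pregnancy reported urgently.

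What is at stake is fetal safety. Cobimetinib, the drug with the listed teratogenic risk, is given at all three dose levels (Table 1). Little in the schedule would pick up a pregnancy in those two months. Testing is at screening only, and the end-of-study visit falls within 28 days of the last dose. General adverse-event collection ends at 30 days, and follow-up for serious events and events of special interest ends 90 days after atezolizumab (Section 9.4.5.1). Later telephone contacts are described as collecting new anti-cancer therapy and survival status (Section 7.4). Contraception is therefore the main safeguard in this period.

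**Working it through.** The plan states no figure to reproduce. The check sets the two periods side by side and then asks whether anything in the documents selects a duration.

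**Inputs**

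| Item | Value | Source |
|---|---|---|
| Contraception, women | at least 3 months after last dose of study drug | Section 5.1, item 8 |
| Pregnancy reporting, female patients | to 5 months after last dose of study drug | Section 9.4.1.5 |
| Live-vaccine restriction | to 5 months after last atezolizumab | Section 5.2, item 26; Section 7.2.2 |
| Hydroxychloroquine half-life | 22.4 days (blood), 123.5 days (plasma) | Section 10.1.1 |
| Women targeted, Phase 1 | 7 of 18 | Table 3 |
| Phase 2 size | 66 to 157 | Section 4.2 |

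**Gap.** 5 − 3 = 2 months. The starting event is the same, so no assumption is needed. The word minimum in item 8 permits longer contraception but does not require it. With item 8 at 5 months, the gap is 5 − 5 = 0.

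**Do the half-lives select a duration?** Assume first-order elimination and 30.44 days per month. Fraction remaining = 2^(−t / half-life).

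- 3 months, t = 3 × 30.44 = 91.3 days. Blood: 2^(−91.3/22.4) = 5.9%. Plasma: 2^(−91.3/123.5) = 59.9%.
- 5 months, t = 5 × 30.44 = 152.2 days. Blood: 2^(−152.2/22.4) = 0.9%. Plasma: 2^(−152.2/123.5) = 42.6%.

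The two half-lives give very different answers, and neither marks 3 or 5 months as the right place to stop.

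**Do the other passages select a duration?** Section 8.3.1 supports contraception in general but gives no period. The vaccine rule applies only where atezolizumab is given (Dose Levels 2 and 3) and is not a reproductive precaution. The only reproductive period longer than 3 months is the 5-month window in Section 9.4.1.5.

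**How many women?** Table 3 gives 7 women and does not say how many are of childbearing potential, so the Phase 1 range is 0 to 7. For Phase 2 the number is an unknown part of 66 to 157 patients. The documents give no basis for computing a risk of conception or of fetal harm.

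**The case against.** The strongest case on the other side is that no rule is broken. Item 8 is an eligibility undertaking and Section 9.4.1.5 is surveillance. A surveillance window may properly outlast the precaution it monitors, and the wider window is the conservative choice. Section 9.4.1.6 sets no end date for reporting a congenital anomaly in a later-conceived child, so reporting periods cannot in general define contraception periods. Section 9.4.4 says that pregnancy reports are not in themselves serious events. All of this stands. A reader might infer that the protocol contradicts itself, and the documents do not support that.

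A reader might also infer that 3 months has been shown to be unsafe. That is not supported either. The risk statement carries no duration, the half-lives favour neither figure, and the vaccine rule concerns something else. The 5-month figure could even be the stray one, since Section 9.4.1.5 names a collaborator mentioned nowhere else in the visible text, which may be a sign of carried-over wording. This is why the figure has to be confirmed in the Investigator's Brochures. It does not supply the missing reason for 3 months.

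Exposure is also limited. Patients have advanced disease, and Section 2.3 cites median survival of 6.1 months on second-line treatment in pancreatic cancer and 7.8 to 8.8 months on later-line treatment in colorectal cancer. Phase 2 needs a further amendment before it opens. Conception in this period will be uncommon. Even so, the protocol admits women from age 18 with performance status 0 or 1 and itself requires contraception, so only the duration is in question.

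Finally, men are asked for contraception for up to 3 months (item 9), and partner pregnancies are also reportable. Those reports have no stated 5-month window, so the mismatch described here concerns female patients.

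**Conclusion.** The point holds as a low-magnitude alignment of safety precautions. Item 8 ends contraception 2 months before the protocol's own pregnancy window closes, with no reason given, in a regimen where one drug carries a listed potential for teratogenicity. Reading the 5-month window as a sign that exposure in that period is considered possible is an inference from Section 9.4.4, which links reports to possible fetal exposure. The protocol does not say so directly.

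The 2-month gap is certain from the text. The number of women affected is not known (0 to 7 in Phase 1), and whether 5 months is long enough cannot be settled from these documents. Sample size, error rates and the primary analyses are untouched.

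**What to change.** In Section 5.1, item 8, replace the 3-month minimum with a 5-month minimum, still counted from the last dose of study drug, and leave the window in Section 9.4.1.5 as it is. This matches the pregnancy window and the 5-month restriction that patients given atezolizumab already observe for live vaccines.

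Confirm the figure against the current Investigator's Brochures, bring the consent form into line, and lengthen the period if the brochures require more. If the sponsor prefers to keep 3 months, item 8 should say why.

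The cost is a one-line amendment, a document check, and two more months of contraception for women of childbearing potential.

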5.2 Exclusion Criteria

Specific exclusion criteria are:

1. Prior treatment with investigational therapy.

Participants may not have had any treatments with investigational therapy within the 28 days prior to initiation of study treatment.

2. Prior radiation therapy

Participants may not have had radiation therapy within 2 weeks prior to initiation of study treatment. Participants may not have had previous radiotherapy to 25% or more of the bone marrow.

3. Prior Therapy

Participants may not have had systemic chemotherapy within 14 days or 5 half-lives of the drug (whichever is longer) prior to initiation of study treatment.

In addition, the following prior treatment is not allowed during **Phase 1** of the study:

- Receptor tyrosine kinase inhibitors targeting MAP kinase pathway;

Columbia University Irving Medical Center
Herbert Irving Comprehensive Cancer Center
AAAS4165_Version Date: 07/07/2021

- Any pharmacological agents inhibiting the autophagy pathway.

In addition, the following prior treatment is not allowed during **Phase 2** of the study:

- T-cell co-stimulating agents or immune checkpoint blockade therapies, including but not limited to anti-CTLA-4, anti-PD-1, and anti-PD-L1 therapeutic antibodies;
- Receptor tyrosine kinase inhibitors targeting MAP kinase pathway;
- Any pharmacological agents inhibiting the autophagy pathway.

4. Adverse events from prior anti-cancer therapy

Participants may not initiate treatment if they have adverse events from prior anti-cancer therapy that have not resolved to Grade ≤ 1 or better, with the exception of Grade ≤ 2 peripheral neuropathy or any grade alopecia.

5. Patients currently receiving any other investigational agents
6. Concomitant treatment with other anti-neoplastic agents (hormone therapy acceptable)
7. Uncontrolled pleural effusion, pericardial effusion, or ascites
8. Patients with symptomatic brain metastases

Subjects with untreated brain metastasis ≤ 1 cm can be considered eligible if deemed asymptomatic by the investigator upon consultation with the medical monitor, and do not require immediate radiation or steroids. Subjects with brain metastasis that is treated and stable for 1 month may be considered eligible if they are asymptomatic and on stable dose of steroids, or if they do not require steroids following successful local therapy.

9. Uncontrolled hypercalcemia (ionized calcium > 1.5 mmol/L, calcium > 12 mg/dL, or corrected serum calcium $>$ ULN) or symptomatic hypercalcemia requiring continued use of bisphosphonate therapy.
10. Recent major surgery or significant traumatic injury

Participants may not have undergone major surgery or experienced significant traumatic injury within 14 days prior to initiating study treatment, or be recovering from a procedure related to adverse events of \leq Grade 1.

11. Active or history of autoimmune disease or immune deficiency

Includes, but is not limited to, myasthenia gravis, myositis, autoimmune hepatitis, systemic lupus erythematosus, rheumatoid arthritis, inflammatory bowel disease, antiphospholipid antibody syndrome, Wegener granulomatosis, Sjögren's syndrome, Guillain-Barré syndrome, or multiple sclerosis, with the following exceptions:

- Patients with a history of autoimmune-related hypothyroidism who are on stable thyroid-replacement hormone are eligible for the study.
- Patients with controlled Type 1 diabetes mellitus who are on a stable insulin regimen

Columbia University Irving Medical Center
Herbert Irving Comprehensive Cancer Center
AAAS4165_Version Date: 07/07/2021

are eligible for the study.

- Patients with eczema, psoriasis, lichen simplex chronicus, or vitiligo with dermatologic manifestations only (e.g., patients with psoriatic arthritis are excluded) are eligible for the study provided all of following conditions are met:
 - Rash must cover <10% of body surface area;
 - Disease is well-controlled at baseline and requires only low-potency topical corticosteroids;
 - No occurrence of acute exacerbations of the underlying condition requiring psoralen plus ultraviolet A radiation, methotrexate, retinoids, biologic agents, oral calcineurin inhibitors, or high-potency or oral corticosteroids within the previous 12 months.

12. History of idiopathic pulmonary fibrosis, interstitial lung disease, organizing pneumonia (e.g., bronchiolitis obliterans), drug-induced pneumonitis, or idiopathic pneumonitis, or evidence of active pneumonitis on screening chest computed tomography scan [history of radiation pneumonitis in the radiation field (fibrosis) is permitted].

13. Positive for HIV at screening or any time prior to screening

Patients without prior positive HIV test result will undergo an HIV test at screening, unless not permitted under local regulations.

14. Active Hepatitis B virus (HBV) infection (chronic or acute)

Defined as having a positive hepatitis B surface antigen (HBsAg) test at screening. Patients with a past or resolved HBV infection, defined as having a negative HBsAg test and a positive total hepatitis B core antibody test at screening, are eligible for the study.

15. Active hepatitis C virus (HCV) infection

Defined as positive HCV antibody test followed by a positive HCV RNA test at screening. The HCV RNA test will be performed only for patients who have a positive HCV antibody test.

16. Known clinically significant liver disease, including alcoholic hepatitis, cirrhosis, fatty liver disease, and inherited liver disease

17. Active tuberculosis

18. Severe infection

Patients may not have had a severe infection within 4 weeks prior to initiation of study treatment. This includes, but is not limited to, hospitalization for complications of infection, bacteremia, or severe pneumonia. However, patients who were admitted for biliary tract infection due to bile duct obstruction at time of diagnosis must have a functioning biliary stent (as evidenced by declining total bilirubin and $\leq 2X$ ULN) and resolved infection (defined by normalization of elevated white blood cell count, absence of signs of infection) and completion of an antibiotic course (at least a seven-day course) prior to initiation of therapy.

Columbia University Irving Medical Center
Herbert Irving Comprehensive Cancer Center
AAAS4165_Version Date: 07/07/2021

19. Recent antibiotic treatment

Patients may not have been treated with therapeutic oral or intravenous (IV) antibiotics within 2 weeks prior to initiation of study treatment, except for biliary tract infection due to bile duct obstruction from the pancreas mass. Patients receiving prophylactic antibiotics (e.g., to prevent a urinary tract infection or chronic obstructive pulmonary disease exacerbation) are eligible for the study.

20. Significant cardiovascular disease

Patient may not have significant cardiovascular disease (such as New York Heart Association Class II or greater cardiac disease, myocardial infarction, or cerebrovascular accident) within 12 months prior to initiation of study treatment, seizure disorder, uncontrolled hypertension, or unstable arrhythmia or unstable angina within 3 months prior to initiation of study treatment.

21. Left ventricular ejection fraction below institutional lower limit of normal or below 50%, whichever is lower

22. Baseline QTcF \geq 450 ms (males) or \geq 470 ms (females)

23. Grade \geq 3 hemorrhage or bleeding event within 28 days prior to initiation of study treatment

24. Prior autologous stem cell, allogeneic stem cell, or solid organ transplantation

25. History of malignancy

Patient may not have a history of malignancy other than PDA within 2 years prior to screening, with the exception of those with a negligible risk of metastasis or death (e.g., 5-year overall survival of $> 90\%$), such as adequately treated carcinoma *in situ* of the cervix, non-melanoma skin carcinoma, localized prostate cancer, ductal carcinoma *in situ*, or Stage I uterine cancer.

26. Recent vaccination

Patients may not have been treated with a live, attenuated vaccine within 4 weeks prior to initiation of study treatment, or anticipate the need for such a vaccine during treatment with atezolizumab or within 5 months after the last dose of atezolizumab.

27. History of severe allergic anaphylactic reactions to chimeric or humanized antibodies or fusion proteins

28. Known allergy or hypersensitivity to 4-aminoquinoline compounds or any of the study drug excipients

29. Recent immunosuppressive treatment

Patients may not have been treated with systemic immunosuppressive medication (including, but not limited to, corticosteroids, cyclophosphamide, azathioprine, methotrexate, thalidomide, and anti-tumor necrosis factor alpha agents) within 2 weeks prior to initiation of study treatment, or

Columbia University Irving Medical Center
Herbert Irving Comprehensive Cancer Center
AAAS4165_Version Date: 07/07/2021

anticipate the need for systemic immunosuppressive medication during the course of the study, with the following exceptions:

- Patients who received mineralocorticoids (e.g., fludrocortisone), corticosteroids for chronic obstructive pulmonary disease or asthma, or low-dose corticosteroids for orthostatic hypotension or adrenal insufficiency are eligible for the study if receiving equivalent to < 10mg of prednisone daily.
- Patients who received a one-time pulse dose of systemic immunosuppressant medication are eligible for the study after approval from the Principal Investigator.

30. Inability to swallow medication or malabsorption condition that would alter the absorption of orally administered medications

31. History of retinal pathology

Patients may not have a history of or evidence of retinal pathology on ophthalmologic examination that is considered a risk factor for neurosensory retinal detachment, central serous chorioretinopathy, retinal vein occlusion (RVO), or neovascular macular degeneration. Specifically, patients will be excluded from study participation if they currently are known to have any risk factors for RVO, including:

- Glaucoma with intraocular pressure ≥ 21 mmHg;
- Grade ≥ 2 serum cholesterol;
- Grade ≥ 2 hypertriglyceridemia;
- Grade ≥ 2 uncontrolled hypertension (patients with a history of hypertension controlled with anti-hypertensive medication to Grade ≤ 1 are eligible).

32. Pregnancy

Pregnant women are excluded from this study because there is an unknown, but potential risk for AEs in nursing infants secondary to treatment of the mother with these agents; breastfeeding should be discontinued.

33. Other contraindicated conditions

Any other disease, metabolic dysfunction, physical examination finding, or clinical laboratory finding that contraindicates the use of an investigational drug, may affect the interpretation of the results, or may render the patient at high risk from treatment complications in the opinion of the treating investigator.

34. Concomitant strong CYP3A4 inhibitors and inducers

Refer to list of common CYP3A4 inhibitors and inducers (Appendix 2). These include anticonvulsants, mycin antimicrobials, and antiretrovirals. Some common examples include inhibitors, such as erythromycin, fluoxetine, gemfibrozil, and inducers, such as rifampicin, carbamazepine, phenytoin, efavirenz, and nevirapine. Concomitant treatment is permitted if the

Columbia University Irving Medical Center
Herbert Irving Comprehensive Cancer Center
AAAS4165_Version Date: 07/07/2021

medication is not expected to interfere with the evaluation of safety or efficacy of the study drug. During the study, if the use of any concomitant treatment becomes necessary (e.g., for treatment of an adverse event), the treatment must be recorded on the eCRF, including the reason for treatment, generic name of the drug, dosage, route, and start and stop dates of administration.

35. Uncontrolled psoriasis, porphyria, proximal myopathy or neuropathy

36. Severe depression

Subjects hospitalized for depression within the past 2 years, or who have prior suicidal attempts will be excluded.

37. Gluocose-6-phosphate dehydrogenase (G-6-PD) deficiency

38. History of connective tissue disorders (e.g., lupus, scleroderma, arteritis nodosa)

39. Subjects on greater than once daily dose of antacid therapy

40. Concomitant use of any of the following drugs:

- Digoxin
- Pharmacological agents known to prolong QT interval
- Mefloquine or other agents which may lower the convulsive threshold
- Antiepileptics
- Methotrexate
- Cyclosporine
- Ampicillin
- Cimetidine

